INVESTIGATOR STUDY PLAN- REQUIRED

Study Protocol

An open-label, feasibility trial of adjunctive telmisartan in patients with treatment resistant schizophrenia

[name], MPH

Identifier: NCT03868839

Document Date: 06/11/2018

A. BACKGROUND

1. Treatment resistant schizophrenia (TRS): TRS, which affects approximately 1/3 of patients with schizophrenia (Meltzer 1997). Currently available antipsychotic agents all fall into the “D2, me too” category. However, the abnormal presynaptic dopamine transmission usually seen in schizophrenia are absent in TRS (Demjaha et al 2012). Novel treatment approaches targeting alternative neural circuits or pathways are urgently needed.

Increased glutamate levels have been reported in antipsychotic-naïve or free patients with schizophrenia (de la Fuente-Sandoval et al 2013, Kraguljac et al 2013). Some studies suggested that antipsychotic treatment may reduce brain glutamate to the levels similar as in healthy controls (de la Fuente-Sandoval et al 2013, Kegeles et al 2012). However, recent studies found higher glutamate levels in the anterior cingulate cortex of antipsychotic-treated first episode patients with unremitted psychotic symptoms, and in treatment-resistant patients than in medication responders (Demjaha et al 2014, Egerton et al 2012). Abnormal glutamatergic signaling secondary to excessive stimulation of non-NMDA glutamate receptors (i.e., AMPA and kainate) may result in calcium influx and neuronal injury, which likely lead to clinical symptoms including cognitive impairment in patients with schizophrenia (Deutsch et al 2001).

3. Telmisartan, inflammation and oxidative stress: Studies have demonstrated that blockade of AT1R by telmisartan reduces inflammation, apoptosis, and oxidative stress (Jung et al 2007, Sato et al 2014). In addition, telmisartan activates the nuclear receptor peroxisome proliferator-activated receptor γ (PPAR γ), which regulates multiple pathways to counteract inflammation and oxidative stress, and promote neuroprotection (Min et al 2012, Pang et al 2012).

4. Potential benefit of telmisartan in schizophrenia: We recently reported that adjunctive treatment with telmisartan improves schizophrenia symptoms (Fan et al 2017). We now further propose to examine whether telmisartan targets glutamatergic signaling in the brain with neuroimaging to measure concentrations of cerebral glutamate metabolites in patients with TRS.

We propose a 4-week, open-label, feasibility trial of adjunctive telmisartan in adult patients with TRS. We plan to recruit 10 patients. All patients will receive telmisartan 80mg daily for 4 weeks.

B. SPECIFIC AIMS

Primary

1. Evaluate changes in blood biomarkers for inflammation and oxidative stress.

C. STUDY DESIGN

Screening visit: After signing a HIPAA compliant informed consent form, subjects will undergo a review of medical history and concomitant medications, and a physical exam. The MINI International Neuropsychiatric Interview will be performed to confirm the psychiatric diagnosis. Subjects will also have a urine drug screen, urine pregnancy test, a complete blood count (CBC), complete metabolic panel (CMP), vital signs, 12-lead ECG.

Baseline visit: After the screening visit, eligible subjects will undergo: 1) vital signs; 2) efficacy assessment battery; 3) safety assessment battery; 4) blood biomarkers for inflammation and oxidative stress, including glutathione (GSH), glutathione disulfide (GSSG), high sensitivity C reactive protein (hsCRP), interleukin 6 (IL-6) and tumor necrosis factor α (TNF α).

Week 1, 2, 3 visits: Vital signs will be assessed. Treatment compliance and possible adverse effects will be evaluated. Subjects will receive one week supply of study medication. Urine drug screen will be repeated at week 2 only.

Week 4 visit: Subjects will undergo: 1) vital signs; 2) efficacy assessment battery; 3) safety assessment battery; 4) blood biomarkers for inflammation and oxidative stress, including GSH, GSSG, hsCRP, IL-6 and TNF α . Lab samples for CBC and CMP will also be collected.

Early termination visit: Subjects will undergo: 1) vital signs; 2) safety assessment battery; 3) CBC and CMP.

D. STUDY POPULATION

Subject eligibility

Inclusion Criteria

Each subject must meet all of the following criteria to be eligible for this study:

1. Age 18-65 years inclusive.
2. Primary diagnosis of Schizophrenia established by a structured psychiatric evaluation (MINI) based on Diagnostic and Statistical Manual of Mental Disorders Fifth Edition (DSM-V) criteria.
3. A Positive and Negative Syndrome Scale (PANSS) (Kay et al 1987) total score ≥ 70 with a score of ≥ 4 on two or more of the following PANSS items: delusions, conceptual disorganization, hallucinatory behavior, suspiciousness, and unusual thought content.
4. A score of ≥ 4 on the Clinical Global Impression—Severity (CGI-S) (Guy, 1976).
5. Must have ongoing antipsychotic treatment for at least 8 weeks, with a stable dose for at least 4 weeks. Subjects who have failed to achieve clinically-recognized symptom reduction to at least 1 marketed antipsychotic agent, given at a Physician Desk Reference (PDR)-defined therapeutic dose for ≥ 8 weeks during the past 12 months, will be eligible.
6. Women of childbearing potential must have a negative pregnancy test performed at screening visit prior to randomization. Women enrolled in this trial must use adequate birth control.
7. Understands and is able, willing, and (in the opinion of the investigator) likely to fully comply with the study procedures and restrictions.

Exclusionary Criteria

Subjects who meet any of the following criteria will be excluded from the study:

1. Psychiatrically unstable.
2. Subjects with any clinically significant abnormalities as determined by medical history, physical exam, clinical and lab evaluation suggestive of an underlying disease state that may, in the opinion of the investigator, confound the results of study, increase risk to the subject, or lead to difficulty complying with the protocol.
3. Current insulin treatment for diabetes.
4. History of immunosuppression.
5. Current or recent radiation or chemotherapy treatment for cancer.
6. Chronic use of steroids (except local use or inhaler).
7. Pregnancy or breastfeeding.
8. Use of diuretics, ACE inhibitors, spironolactone, potassium supplements, digoxin or warfarin because of the possible drug-drug interaction with telmisartan.
9. Tested positive for the urine drug screen.

10. Subjects at imminent risk of suicide or injury to self or others, as per the opinion of the investigator, or history of significant suicide attempt within the last 6 months as per the Columbia Suicide Severity Rating Scale (C-SSRS).
11. Subjects that have taken an investigational drug or taken part in a clinical trial within 30 days prior to screening.
12. Subjects with a current (within the last 3 months) DSM-V diagnosis of alcohol or substance use disorder (excluding nicotine and caffeine) as established by the clinical assessment (MINI) at the screening visit will be excluded.
13. Any other reason that, in the opinion of the investigator, would compromise patient safety or integrity of the study.
14. Subjects with the lab values defined as exclusionary safety values in Table 1.

Table 1. Exclusionary Safety Values of Potential Clinical Concern

Complete Blood Count	
Leukocytes	<2 or >17.5 x 10 ³ /mm ³
Platelets	<75 or >700 x 10 ³ /mm ³
Comprehensive Metabolic Panel	
Sodium	<1.1 times the lower limit or >1.1 times upper limit of the reference
Potassium	<1.1 times the lower limit or >1.1 times upper limit of the reference
Blood Urea Nitrogen (BUN)	>1.3 times upper limit of the reference range
Creatinine	>1.3 times upper limit of the reference range
Glomerular Filtration Rate	< 60
Aspartate amino transferase (AST)	>3 times upper limit of the reference range
Alanine amino transferase (ALT)	>3 times upper limit of the reference range

E. ASSESSMENT PROCEDURES

Medical history

A detailed medical history will be obtained by the PI or designee during the screening visit. This will include information regarding the subject' full history of medical and psychiatric conditions, diagnoses, procedures, treatments, demographic information, and any other noteworthy medical information, including suicidality, with dates of start and finish. Any updates to medical history information that the PI or designee becomes aware of will be captured throughout the study.

Physical exam

The PI, or medically qualified designee, will perform the physical exam at the screening visit. If any clinically significant change is noted from screening, it will be reported as an adverse event and will be followed up to resolution or upon reaching a stable endpoint.

Vital signs

Evaluation of vital signs will be performed by qualified personnel after the subject has been supine for 5 minutes, and will include a measurement of systolic and diastolic blood pressure, pulse rate, and oral temperature. Systolic and diastolic blood pressure should be then measured from supine to standing to assess orthostatic hypotension. Vital sign measurements will be obtained at the time points indicated in the schedule of events (SOE).

If clinically significant findings, as determined by the PI or medically qualified designee, occur in any vital sign measurement, that measurement should be captured as an adverse event and will be repeated at medically appropriate intervals until the value returns to an acceptable range, a specific diagnosis is established, or the condition is otherwise explained.

Laboratory assays

Fasting blood samples will be obtained and laboratory tests will be performed at the time points indicated in the SOE.

Complete blood count (CBC): White blood cell (WBC) count with differential (absolute neutrophil count, lymphocytes, monocytes, basophils, and eosinophils), red blood cell (RBC) count, hemoglobin (Hgb), hematocrit (Hct), and platelet count.

Comprehensive metabolic panel (CMP): glucose, sodium, potassium, calcium, chloride, carbon dioxide, blood urea nitrogen (BUN), creatinine, calculated glomerular filtration rate, uric acid, phosphorus, magnesium, total protein, albumin, aspartate amino transferase (AST), alanine amino transferase (ALT), alkaline phosphatase (ALP), total bilirubin.

Blood levels of GSH, GSSG, hsCRP, IL-6, TNF α : Blood samples for GSH, GSSG, hsCRP, IL6 and TNF-alpha will be run at the UMass Memorial labs.

The PI, or medically qualified designee, should mark either “CS” for Clinically Significant or “NCS” for Not Clinically Significant in the margin of the laboratory result source document for items outside the normal range.

Urine drug screen: The test includes the following substances: opioids, cocaine, amphetamines, methadone, cannabinoids, barbiturates, benzodiazepines, methamphetamine, and phencyclidine.

Urine pregnancy test: The test will be performed in female subjects of childbearing potential using a dipstick urine test during the screening visit.

12-Lead Electrocardiogram (EGG)

A 12-lead ECG will be taken at following a supine rest for 5 minutes. The ECGs will be reviewed by the PI or medically qualified designee, and a cardiologist to assess any immediate abnormalities. The findings of the ECGs will be marked as normal, abnormal-not clinically significant, or abnormal-clinically significant.

Psychiatric diagnostic assessment

Mini International Neuropsychiatric Interview (MINI v7.0): The MINI 7.0 is a short clinician administered structured diagnostic interview for major psychiatric diagnoses in DSM-5 with an administration of around 20 minutes.

Efficacy assessment battery

The Positive and Negative Syndrome Scale (PANSS) (KAY ET AL 1987): The PANSS will be used to measure symptom severity in this trial. The PANSS is a 30-item questionnaire used to evaluate schizophrenia symptoms, based on the clinical interview as well as reports of family members or primary care hospital workers. The PANSS consists of Positive Symptom subscale (7 items), Negative Symptom subscale (7 items), and General Psychopathology subscale (16 items). Each item is scored on a 7-point scale with higher scores representing increasing levels

of psychopathology: 1) Absent, 2) Minimal, 3) Mild, 4) Moderate, 5) Moderate severe, 6) Severe, and 7) Extreme.

Scale for Assessment of Negative Symptoms (SANS) (Andreasen 1989): The SANS assesses 5 domains: affective flattening, alogia, avolition/apathy, anhedonia/asociality, and attention. Within each domain, separate symptoms are related from 0 (absent) to 5 (severe).

Clinical Global Impressions–Severity (CGI-S) and Clinical Global Impressions–Improvement (CGI-I) Scales (Guy, 1976): The CGI-S is an observer-rated scale that measures illness severity. The severity is measured using a 7 point Likert scale: 1) Normal, not at all ill, 2) Borderline mentally ill, 3) Mildly ill, 4) Moderately ill, 5) Markedly ill, 6) Severely ill, and 7) Among the most extremely ill patient. The CGI-I is an observer-rated scale that measures illness improvement. Improvement is measured using a 7 point Likert scale: 1) Very much improved, 2) Much improved, 3) Minimally improved, 4) No change 5) Minimally worse, 6) Much worse, 7) Very much worse.

Safety assessment battery

Adverse Events (AE): Adverse events will be monitored at each study visit. The PI or medically qualified designee will review adverse events at every study visit. AE information is collected and recorded starting on the day the consent is signed until the end of an individual’s participation in the study.

The Columbia Suicide Severity Rating Scale (C-SSRS) (Posner et al 2007): The C-SSRS is a low-burden measure of the spectrum of suicidal ideation and behavior that was developed in the National Institute of Mental Health Treatment of Adolescent Suicide Attempters Study to assess severity and track suicidal events through any treatment. It is a clinical interview providing a summary of both ideation and behavior that can be administered during any evaluation or risk assessment to identify the level and type of suicidality present. The C-SSRS can also be used during treatment to monitor for clinical worsening. The C-SSRS will be performed to assess suicidal ideation and behavior. It contains a 1-to-5 rating scale for suicidal ideation of increasing severity (from a “wish list to die” to an “active thought of killing oneself with plan and intent”). The time frame is the past six months for the Baseline/Screening scale and since the last visit for the Since Last Visit scale.

Monitoring and Reporting of Adverse Events

Continuous data and safety monitoring will be conducted by the PI. Any adverse effect reported to study personnel will be reviewed with the PI or sub-investigator who will determine whether they are mild, moderate or severe and the likelihood (definitely/possible/probable) that it is related to the study medication. All AEs will be followed until resolution, until deemed stable by the investigator or until the subject is deemed by the investigator to be lost to follow-up

Intensity	Definition
Mild	Causes transient or mild discomfort ; no limitation of usual activities; no medical intervention required.
Moderate	Causes mild to moderate limitation in activity; some limitation of usual activities: no or minimal medical intervention or therapy is required.
Severe	Causes marked limitation in activity; some assistance is usually required; medical intervention or therapy is required; hospitalization is probable.

The PI is ultimately responsible for assessing and reporting all adverse events as outlined in the study plan. The assessment of AEs may be delegated to a medically qualified Sub-Investigator, trained on this study plan. The PI will report adverse events to the IRB in accordance with IRB guidelines.

Reporting of Serious Adverse Events

The PI will report all SAEs to UMass IRB. The PI will inform the IRB regarding any AE (does not have to be causally related) that is both serious and unexpected; or that represents a series of AEs that, on analysis, is unanticipated, or occurs at an unanticipated frequency, or otherwise represents an unanticipated safety risk to the study subject in accordance with UMass IRB reporting guidelines.

F. TREATMENT

Dosing

Subjects will start telmisartan 40mg once a day during week 1; the dose will be increased to 80mg (target dose) or as tolerated during the remaining weeks.

Study medication Supplies and Administration

Telmisartan has 20mg, 40mg and 80mg dose strengths. Subjects will be given one 40mg pill per day during week 1, and one 40mg pill plus two 20mg pills per day for the remaining weeks.

Potential risks of telmisartan

When telmisartan was co-administered with digoxin, median increases in digoxin peak plasma concentration (49%) and in trough concentration (20%) were observed. It is therefore recommended that digoxin levels be monitored when initiating, adjusting, and discontinuing telmisartan. Telmisartan administered for 10 days slightly decreased the mean warfarin trough plasma concentration; this decrease did not result in a change in International Normalized Ratio (INR). Telmisartan can cause fetal and neonatal morbidity and death when administered to pregnant women. In volume- and/or salt-depleted patients (e.g., those being treated with high doses of diuretics), symptomatic hypotension may occur after initiation of therapy with telmisartan. Adverse events occurring at an incidence of 1% or more in patients treated with telmisartan and at a greater rate than in patients treated with placebo, irrespective of their causal association, include upper respiratory tract infection, back pain, sinusitis, diarrhea and pharyngitis. Common adverse experiences have generally been mild and transient in nature and have only infrequently required discontinuation of therapy. In placebo-controlled trials involving 1,041 patients treated with various doses of telmisartan (20-160mg) monotherapy for up to 12 weeks, an overall incidence of adverse events similar to that of placebo was observed. (Micardis® package insert, revised, February 2018).

For the proposed study, patients will be excluded if they are on diuretics, ACE inhibitors, digoxin or warfarin because the possible drug-drug interaction with telmisartan. Subjects will be excluded from the study if they have an abnormal potassium blood level out of the defined cutoff range at screening. Subjects will be terminated from the study if they have an abnormal potassium blood level at screening. For female patients of childbearing potential, a urine pregnancy test must be negative at screening. These patients must agree to practice appropriate birth control methods during the study.

Discontinuation from Study Treatment

The reasons for early discontinuation include the following: 1) request of patient, 2) decision of the PI, 3) serious adverse event.

Procedures for discontinuation from study

If a patient discontinues from the study before randomization, then no further follow-up will be expected. However, if the patient discontinues after randomization, but before receiving any study treatment, the patient will be asked to return for a final study visit, during which the procedures outlined in the early termination visit procedures will be completed, including AEs and concomitant medication assessments.

If a patient discontinues from the study before completion and has received the dose of study drug, the patient will be asked to return for a final study visit, at which the procedures outlined in the early termination visit will be completed. Every effort will be made to follow up with patients who discontinue from the study. If the patient refuses follow-up, the reason for the refusal and last contact date should be documented in the CRF.

G. ETHICAL CONSIDERATION

Informed consent

The investigator must ensure that patients are clearly and fully informed about the purpose, potential risks, and other critical issues regarding clinical trials in which they volunteer to participate.

All subjects will receive the consent form for the study. Any questions, concerns, or ambiguities will be clarified by the PI or medically qualified designee prior to the patient signing consent. Subjects will sign informed consent and only then will begin participation in the study.

IRB review

Before study initiation, the investigator will have written and dated approval from the UMass IRB for the protocol, consent form, patient recruitment materials and process (e.g., advertisements), and any other written information to be provided to subjects.

The investigator will provide the IRB with reports, updates, and other information (e.g., safety updates, amendments) according to regulatory requirements and institution procedures.

H. DATA ANALYSIS

There are no published data yet about the effect of telmisartan treatment on the levels of glutamate and GABA in the brain in patients with schizophrenia. The study is intended to provide preliminary evidence of target engagement in the brain, as well as an indication of effect size for the purpose of designing future studies. Paired sample t tests will be used to examine the difference in outcome measures between week 4 and baseline. In addition, Pearson correlation analysis or partial correlation analysis will be used to examine the relationship between changes in biomarkers and changes in symptom outcome measures.

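### The early termination visit omits the biomarkers, PANSS and SANS, so a treated patient who leaves before Week 4 has no post-baseline value for the only stated aim

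*Protocol*

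**What the plan says.** The single aim in protocol section B is "Evaluate changes in blood biomarkers for inflammation and oxidative stress". Section H tests it with paired t-tests of Week 4 against baseline and correlates biomarker changes with symptom changes. The SAP names only a paired t-test. Neither document has a rule for missing Week 4 values.

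For early leavers, section C of the protocol and the Procedures part of the SAP give the same list: "Early termination visit: Subjects will undergo: 1) vital signs; 2) safety assessment battery; 3) CBC and CMP". The Schedule of Events agrees. Its biomarker, PANSS and SANS rows are marked at Baseline and Week 4 only, while the CBC/CMP row is also marked at early termination. CGI is rated weekly but not at early termination.

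Section F lists why patients may leave: "The reasons for early discontinuation include the following: 1) request of patient, 2) decision of the PI, 3) serious adverse event". A treated patient who leaves is asked back for a final visit "at which the procedures outlined in the early termination visit will be completed". The same section adds: "Every effort will be made to follow up with patients who discontinue from the study". It names no biomarker or rating to be taken and does not ask the patient to attend Week 4.

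**The concern.** A paired test needs two values, and Week 4 is the only scheduled source of the second. Following the plan exactly loses the pair for every early leaver, even one who returns and has blood drawn. What remains for that patient is the baseline values, CGI from the weekly visits attended, and exit safety data. None of these is a post-baseline biomarker, PANSS or SANS value.

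Section H says the trial should give "an indication of effect size for the purpose of designing future studies". The listed reasons for leaving could be related to tolerability or response. If leavers change less than completers, a completers-only effect size is too large for planning a study that counts all treated patients. The plan collects no biomarker value that would reveal this.

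**Working it through.** **Is there any other source of a post-baseline value?**

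| Measure | Baseline | Weeks 1–3 | Week 4 | Early termination |
|---|---|---|---|---|
| Five biomarkers | yes | no | yes | no |
| PANSS, SANS | yes | no | yes | no |
| CGI | yes | yes | yes | no |
| CBC, CMP | no (screening) | no | yes | yes |

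There is none for the biomarkers, PANSS or SANS.

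**Inputs.** N = 10 is from the protocol. The documents give no withdrawal rate, SD, effect size or alpha, so there is no planned figure to reproduce. Assumed: two-sided 5%; k = 1 or 2 of 10 leave; completers change by 1 SD; leavers change by g = 0 to 0.5 SD; within-group SD 1.

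**How likely is a loss?** At an assumed 10% withdrawal rate, the chance that at least one of 10 leaves is 1 − 0.9^10 = 65%. At 20% it is 1 − 0.8^10 = 89%.

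**Precision.** Half-width of the 95% CI for mean change, in SD of change, is t(0.975, n−1)/√n:
- n = 10: 2.262/3.162 = 0.715
- n = 9: 2.306/3 = 0.769 (7.5% wider)
- n = 8: 2.365/2.828 = 0.836 (17% wider)

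**Effect size.** Completers show a mean of 1.00 SD. For all 10, mean = ((10−k) + k·g)/10 and SD = √(1 + (k/10)(1−k/10)(1−g)²). The last column is the number of pairs a later study needs for 80% power (noncentral t); it is 10 at an effect of 1.00.

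| k | g | Mean | SD | Standardised effect | Pairs needed |
|---|---|---|---|---|---|
| 1 | 0 | 0.90 | 1.044 | 0.862 | 13 |
| 1 | 0.5 | 0.95 | 1.011 | 0.940 | 11 |
| 2 | 0 | 0.80 | 1.077 | 0.743 | 17 |
| 2 | 0.5 | 0.90 | 1.020 | 0.883 | 13 |

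**Would pooling the recovered values raise power?** Power with 10 pairs is from 1,000,000 simulated trials per case. Power with completers alone is from the noncentral t.

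| k | g = 0 | g = 0.25 | g = 0.5 | Completers alone |
|---|---|---|---|---|
| 1 | 0.682 | 0.721 | 0.754 | 0.748 (n = 9) |
| 2 | 0.551 | 0.632 | 0.702 | 0.681 (n = 8) |

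Interpolating between g = 0.25 and 0.5, break-even is at 0.25 + 0.25 × (0.748 − 0.721)/(0.754 − 0.721) = 0.45 for one leaver and 0.25 + 0.25 × (0.681 − 0.632)/(0.702 − 0.632) = 0.425 for two. Below that, pooling lowers power.

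**The case against.** The case against concedes the omission and disputes what it costs.

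- **An exit value is not the quantity of interest.** Section H also speaks of target engagement in the brain, for which change on drug at Week 4 is the natural measure. An exit sample may be taken off drug, after a serious adverse event, or at the lower dose: "Subjects will start telmisartan 40mg once a day during week 1; the dose will be increased to 80mg (target dose) or as tolerated". A smaller change at exit could simply reflect short exposure. This stands as a reason not to pool exit values, but not as a reason not to collect them. The brain argument has little force, because the schedule contains no brain measure.
- **The main result does not change.** With the Week 4 test kept as the main analysis, the wider interval is the cost of withdrawal and the fix does not remove it. This stands.
- **The shift is small beside the noise.** With an observed effect of 1.0 SD, the exact 95% CI for the standardised effect is 0.21 to 1.75 even with all 10 pairs, which puts the later study anywhere from 175 down to 5 patients. One or two exit values will not settle that. This stands. It limits the benefit to showing a possible bias, which with 10 patients cannot be tested.
- **Nobody may leave.** Treatment is short, visits are weekly, and patients must be judged likely to comply. With no withdrawals the omission costs nothing, so the benefit is conditional.
- **PANSS and SANS are not in the stated aim.** True. They matter for the symptom comparisons and the correlations in section H.

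**Conclusion.** The concern holds. The protocol text, the SAP text and the Schedule of Events agree, and nothing elsewhere supplies a post-baseline biomarker, PANSS or SANS value for an early leaver. If anyone leaves, the paired tests and the correlations rest on completers alone, with no means of checking that figure.

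Under the assumptions above, the mean is overstated by 0.05 to 0.10 SD with one leaver and by 0.10 to 0.20 SD with two. That is well inside a half-width of 0.77 to 0.84 SD. The omission itself is certain. Its numerical effect is modest and depends on k and g, which the documents do not give. The change is worth making because it is cheap and a sample not taken at exit cannot be recovered later.

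**What to change.** 1. Add GSH, GSSG, hsCRP, IL-6, TNF alpha, PANSS, SANS and CGI to the early termination visit in protocol section C, the Schedule of Events and the SAP.
2. In the discontinuation procedures of section F, invite patients who stop early to the Week 4 assessment as a named part of follow-up.
3. Keep the Week 4 paired t-test on available pairs as the main analysis and report the number of pairs. Add a labelled sensitivity analysis that includes exit or off-drug values, and list time on drug and last dose for each such patient.

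**Cost.** Five assays per leaver, so 5 to 10 with one or two leavers, at a visit that already draws blood; twice that if they also attend Week 4. Add rating time and a few sentences of text.

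**Downsides.** Some patients will decline. Others will arrive unfasted, although section E specifies: "Fasting blood samples will be obtained and laboratory tests will be performed at the time points indicated in the SOE". Inflammatory markers drawn after a serious adverse event may reflect that event. For these reasons the values belong in the sensitivity analysis and not in the main test.

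### Table 1 puts the lower sodium and potassium cut-offs above the lower reference limit, so on usual reference ranges no patient with a normal sodium is eligible

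*Protocol*

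**What the plan says.** Protocol section D, Exclusionary Criteria, opens with "Subjects who meet any of the following criteria will be excluded from the study", so meeting one item is enough. Item 14 reads "Subjects with the lab values defined as exclusionary safety values in Table 1". In Table 1 the sodium row and the potassium row carry the same rule: "<1.1 times the lower limit or >1.1 times upper limit of the reference".

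Section F, under the potential risks of telmisartan, relies on the same limits: "Subjects will be excluded from the study if they have an abnormal potassium blood level out of the defined cutoff range at screening". The potassium row of Table 1 is the only such range in either document.

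Neither document gives a laboratory reference range or corrects the multiplier. The SAP's Participants section lists exclusion criteria but leaves out the Table 1 item.

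**The concern.** A low-side safety limit should lie at or below the lower limit of normal. Multiplying that limit by 1.1 puts the cut-off above it, so the rule rejects normal values. The sodium reference range is narrow relative to its level, so a 10% upward shift of the lower limit can pass the upper limit altogether. For potassium the shift removes only the low-normal part.

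At stake is a binding eligibility and safety threshold. If it is followed, the trial turns away patients with normal sodium and admits those above normal. If staff set it aside, every patient with a normal sodium is enrolled against a written exclusion, and decisions on low values have no stated number behind them. The screening value carries weight because, in the Schedule of Events, the next metabolic panel is at week 4 or early termination, while section F raises the dose from 40 mg to 80 mg after week 1.

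**Working it through.** **Inputs from the protocol**
- Rule for sodium and potassium (Table 1): exclude if the value is below 1.1 × LLN or above 1.1 × ULN, where LLN and ULN are the lower and upper reference limits.
- Status: binding through exclusion 14.

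**Inputs assumed**, because the documents give no reference ranges
- Sodium 135-145 mmol/L as the base case, with LLN from 132 to 137 and ULN from 144 to 148 as alternatives.
- Potassium 3.5-5.0 mmol/L as the base case, with LLN from 3.3 to 3.6 and ULN from 4.8 to 5.5 as alternatives.

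**Formulas**
- Eligible window as written: 1.1 × LLN to 1.1 × ULN.
- Share of the normal range's width excluded: (1.1 × LLN − LLN) / (ULN − LLN), capped at 100%.
- The whole normal range is excluded when 1.1 × LLN > ULN, that is, when ULN/LLN < 1.1.

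**Sodium, base case**
- Lower cut-off: 1.1 × 135 = 148.5, above the ULN of 145.
- Upper cut-off: 1.1 × 145 = 159.5.
- ULN/LLN = 145/135 = 1.074, below 1.1.
- The eligible window is 148.5-159.5, all of it above normal.

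**Sodium, other assumed ranges**

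| Range | ULN/LLN | 1.1 × LLN | Normal width excluded |
|---|---|---|---|
| 136-144 | 1.059 | 149.6 | 100% |
| 136-145 | 1.066 | 149.6 | 100% |
| 137-147 | 1.073 | 150.7 | 100% |
| 135-146 | 1.081 | 148.5 | 100% |
| 134-146 | 1.090 | 147.4 | 100% |
| 133-145 | 1.090 | 146.3 | 100% |
| 133-146 | 1.098 | 146.3 | 100% |
| 133-147 | 1.105 | 146.3 | 95% |
| 132-146 | 1.106 | 145.2 | 94% |
| 133-148 | 1.113 | 146.3 | 89% |

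With the base case, 8 of 11 ranges lose every normal value. The other three are unusually wide and keep only a sliver at the top of normal.

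**Potassium, base case**
- Lower cut-off: 1.1 × 3.5 = 3.85. Upper cut-off: 1.1 × 5.0 = 5.50.
- Share of normal width excluded: (3.85 − 3.5) / (5.0 − 3.5) = 0.35/1.5 = 23%.
- Over the alternatives the share runs from 17% (3.3-5.3) to 24% (3.4-4.8).

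**A mechanical swap to 0.9**
- Sodium: 0.9 × 135 = 121.5, giving 121.5-159.5.
- Potassium: 0.9 × 3.5 = 3.15, giving 3.15-5.50.
- Both windows contain the whole normal range, but the sodium window is very wide on both sides.

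**The case against.** **The sodium result needs an outside input.** Total exclusion requires ULN/LLN below 1.1, and the documents do not give the range. That is right, and the conclusion should be read as holding for usual ranges. The exceptions found still lose 89-95% of the normal width, so the rule fails on every range tried.

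**Clinical judgement remains.** Exclusion 2 covers clinically significant laboratory abnormalities, exclusion 13 covers patient safety generally, and section E has the investigator classify out-of-range results by clinical significance. A low sodium or potassium could therefore still be caught if the row were ignored. That stands, so what would be missing is a numeric lower limit rather than all protection. But these provisions can only exclude more patients. None of them permits enrolling someone who meets exclusion 14.

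**The potassium effect is partial and errs towards caution.** The rule turns away low-normal patients and admits nobody with low potassium. The upper limb, at 1.1 × ULN, is coherent and resembles the 1.3 × ULN limits for BUN and creatinine. Nor is 23% of the width 23% of patients: if 3.5-5.0 is taken as the central 95% of a normal distribution (an assumption), about 13% of normal-range patients fall between 3.5 and 3.85. All of this is fair, and the upper limb is not the fault here.

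**It is probably a drafting slip.** The study is small ("We plan to recruit 10 patients") and the documents describe one institution, so staff would probably notice at the first screening and not apply the row literally. The likely outcome is a set of deviations or a clarification, not a cohort with high sodium. The primary aim, the endpoints and the paired t-test are untouched. This limits the practical harm, but the criterion still cannot be followed as written, and staff cannot tell from the text what number was meant.

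**Conclusion.** The concern holds. The lower cut-off for both electrolytes is on the wrong side of the lower reference limit, the rule is binding, and nothing in either document corrects it. For potassium it also works against section F, whose stated purpose is to exclude abnormal values.

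On usual sodium ranges 100% of normal values are excluded and only values above normal are eligible. For potassium, 17-24% of the normal width is excluded over the ranges tried. These sizes depend on the assumed reference ranges. The direction of the error does not, because 1.1 times a positive lower limit always exceeds that limit. The correction is needed before anyone is screened against the table, because this is an eligibility and safety threshold. It does not alter the statistical analysis.

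**What to change.** Replace the lower-limit entry in the sodium and potassium rows of Table 1 with one that falls below the lower reference limit, either as a multiplier under 1 or as absolute values. State explicitly in section F that its potassium cut-off means the corrected potassium row.

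The investigators need to choose the figures on clinical grounds. Changing 1.1 to 0.9 without thought would admit sodium down to 121.5 mmol/L on a 135-145 range, which may not be what they want. Citing the laboratory's reference ranges beside the table would let the resulting windows be checked at a glance.

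The cost is a two-row protocol correction and one cross-reference, with no extra patients, tests or analyses.
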